5.1.3. Transaminase and GGT Elevations

In clinical studies of bardoxolone methyl, almost all patients had increases of transaminase enzymes above baseline upon initiation of treatment, which followed a consistent pattern and have not been associated with elevations in bilirubin or other signs of liver toxicity. In BEACON, fewer hepatobiliary SAEs were observed in the bardoxolone methyl arm than in the placebo arm. The elevations begin immediately after initiation of treatment or an increase in dose and peak approximately two to four weeks later. In most patients, transaminase elevations were mild, but approximately 4 to 11% of patients experienced an elevation to greater than three times the ULN. The elevations resolved to levels less than the ULN in most all patients with elevations, within two weeks after peak values while patients continued taking study drug. Patients who experienced elevations to greater than three times the ULN sometimes required additional time to resolve. While some patients have had elevations to above three times the ULN, persistent elevations to above three times the ULN have not been observed, and the elevations did not recur once resolved, unless caused by other factors.

Bardoxolone methyl regulates GGT, a known Nrf2 target gene. In clinical studies, low level GGT elevations during treatment were common, mild, and typically lasted longer than ALT/AST elevations. Bilirubin levels in patients experiencing transaminase or GGT elevations due to treatment with bardoxolone methyl either remained at baseline levels or decreased. The ALT, AST, and GGT elevations were generally self-limiting in patients who continued treatment with study drug.

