7.5. Schedule of Assessments

Table 3, Table 4, Table 5, and Table 6 list the overall schedule of assessments for the study.

Table 3: Part 1: Schedule of Assessments for Patients in Cohorts 1 and 2

Assessment \ Study Week (Day)	Screen A ^a	Screen B ^a	Day 1 ^b	Week 1 (Phone) Day 3±1	Week 1 ^c Day 7±3	Week 2 (Phone) Day 10±1	Week 2 ^c Day 14±3	Week 3 (Phone) Day 21±3	Week 4 Day 28±3	Week 8 Day 56±3	Week 12 Day 84±3	Week 16 or End of Treatment Visit ^d Day 112±3	Follow-up ^d
Informed consent	X												
Inclusion/ exclusion	X		X ^e										
Demographics and baseline disease characteristics	X												
Concomitant medications	X		X	X	X	X	X	X	X	X	X	X	X
Medical history	X												
Height	X												
Weight in clinic	X		X		X		X		X	X	X	X	X
Weight at home			X ^f	X ^f	X ^f	X ^f	X ^f	X ^f	X ^f	X ^f	X ^f	X ^f	
Dispense weight diary			X		X		X		X	X	X	X	
Collect/review weight diary				X	X	X	X	X	X	X	X	X	
ECG	X											X	X
Vital sign measurements	X		X		X		X		X	X	X	X	X
Physical exam ^g /clinical worsening assessment ^h	X		X		X ⁱ		X ⁱ		X	X	X	X	X
Pregnancy test for WOCBP ^j	X		X									X	X
Study drug administration			X	-----X-----									
Dispense study drug			X						X	X	X		
Collect study drug									X	X	X	X	
Telephone contact				X		X		X					
Adverse event collection			X ^k	X	X	X	X	X	X	X	X	X	X
Clinical chemistry	X		X		X		X		X	X	X	X	X
BNP and NT-Pro BNP ^l	X		X		X		X		X	X	X	X	X
Hematology	X		X		X		X		X	X	X	X	X
Urinalysis and microscopy	X		X		X		X		X	X	X	X	X
Virus serology ^m	X												
6-min walk test	X ⁿ	X ⁿ							X ⁿ	X	X	X ⁿ	X
ECHO ^o	X ^p		X						X			X	
[REDACTED]			[REDACTED]						[REDACTED]			[REDACTED]	
[REDACTED]			[REDACTED]						[REDACTED]			[REDACTED]	
[REDACTED]			[REDACTED]						[REDACTED]			[REDACTED]	
[REDACTED]			[REDACTED]						[REDACTED]			[REDACTED]	

Assessment \ Study Week (Day)	Screen A ^a	Screen B ^a	Day 1 ^b	Week 1 (Phone) Day 3±1	Week 1 ^c Day 7±3	Week 2 (Phone) Day 10±1	Week 2 ^c Day 14±3	Week 3 (Phone) Day 21±3	Week 4 Day 28±3	Week 8 Day 56±3	Week 12 Day 84±3	Week 16 or End of Treatment Visit ^d Day 112±3	Follow-up ^d
24-hour ambulatory blood pressure monitoring (ABPM)		X ^s							X			X	
Pulmonary function testing/ Right Heart Catheterization	X ^t												
[REDACTED]	[REDACTED]	[REDACTED]							[REDACTED]	[REDACTED]	[REDACTED]	[REDACTED]	[REDACTED]
[REDACTED]			[REDACTED]									[REDACTED]	
Functional class assessment ^w	X		X									X	X
PK samples ^x									X				

^a Total screening period should not exceed 28 days.

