^l Patients must be allowed to rest for a minimum period of one hour following arrival at the clinic and prior to collecting this blood sample. Similarly, this sample must be taken prior to the 6MWT. This sample should be taken with the patient in the same position at all appropriate visits, e.g., sitting or semi-recumbent.

^m Tests for hepatitis B and hepatitis C. If the initial hepatitis C result is positive, then the patient will need to return for an unscheduled HCV RNA assessment to determine if the virus is present at the current time. If the results of this test are negative, the patient may continue in the screening process.

ⁿ The 6-minute walk test must be performed on two separate days prior to randomization and on 2 separate days within the Week 4 and Week 16 3-day window.

^o Day 1 ECHO, [REDACTED] can be performed anytime after the patient qualifies (completed Screen A and Screen B) for the study and prior to study drug administration. The Week 4 and 16 ECHO, [REDACTED] assessments must occur within the visit window (+/- 3 days); however, they can be performed on different days than the other visit assessments. [REDACTED]

^p Echocardiography (ECHO) within 60 days prior to Day 1 may be used to determine eligibility [REDACTED]

[figure not shown]

^q [REDACTED]

- ^s Prior to randomization, the patient must have a qualified 24-hour ABPM assessment. If first 24-hour assessment is not qualified, one re-test may be performed prior to randomization. If the second test result does not qualify the patient will be considered a screen failure.
- ^t Pulmonary function tests within 90 days prior to Day 1 may be used to determine eligibility. Right heart catheterization within 36 months prior to Day 1 may be used to determine eligibility.
- ^u Completed immediately following the completion of the 6MWT.
- ^v [REDACTED]
- ^w If clinical worsening is suspected, perform unscheduled functional class assessment.
- ^x Blood samples for PK analysis should be drawn just prior to (0 hour) and after (2 and 4 hours) dose administration for this visit. Patients should be instructed to not take their study drug prior to coming to the clinic at Week 4.

Abbreviations: ECG = electrocardiogram, ECHO = echocardiogram, PK = pharmacokinetic, s = serum, u = urine, WOCBP = women of child-bearing potential, [REDACTED]

[REDACTED] 6MWT = 6-minute walk test

Table 4: Part 1: Schedule of Assessments for Patients in Cohort 3 and Cohort 4 (PH-ILD Cohort)

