- ⁱ Patients who dose escalate must have a telephone call 1 week after dose escalation and an unscheduled office visit or home health 2 weeks (\pm 3 days) after dose escalation to collect clinical chemistry, BNP and NT-Pro BNP, as well as a telephone call.
- ^j Patients must be allowed to rest for a minimum period of one hour following arrival at the clinic and prior to obtaining this blood sample. Similarly, this sample must be taken prior to the 6MWT. This sample should be taken with the patient in the same position at all appropriate visits, e.g., sitting or semi-recumbent.
- ^k After Week 32, only NT-Pro BNP will be collected.
[REDACTED]
- ^m If clinical worsening is suspected, perform unscheduled functional class assessment.
- ⁿ Blood samples for PK analysis should be drawn just prior to (0 hour) and after (2 and 4 hours) dose administration for this visit. Patients should be instructed to not take their study drug prior to coming to the clinic at Week 20.

Abbreviations: ECG = electrocardiogram, ECHO = echocardiogram, PK = pharmacokinetic, s = serum, u = urine, WOCBP = women of child-bearing potential, [REDACTED]
[REDACTED]

Table 6: Part 2: Extension Schedule of Assessments for Patients in Cohorts 3 and 4

Assessment \ Study Week	Week 16 ^a (Day 1) (±3 days)	Week 17 (Phone) (±1 day)	Week 18 ^b (±3 days)	Week 19 (Phone) (±1 day)	Week 20 (±3 days)	Week 21 (Phone) (±1 day)	Week 22 ^b (±3 days)	Week 23 (Phone) (±1 day)	Week 24 ^b (±3 days)	Week 32 (± 5 days)	Week 56 and Every 24 Weeks Thereafter (±5 days) ^c	End of Treatment Visit ^d (± 5 days)	Follow-up ^d (± 5 days)
Concomitant medications		X	X	X	X	X	X	X	X	X	X	X	X
Weight in clinic			X		X		X		X	X	X	X	X
Weight at home ^e		X	X	X	X	X	X	X	X	X	X		
Dispense weight diary	X		X		X		X		X	X	X		
Collect/Review weight diary		X	X	X	X	X	X	X	X	X	X	X	
ECG										X		X	X
Vital sign measurements			X		X		X		X	X	X	X	X
Physical exam/clinical worsening assessment ^f			X ^g		X		X ^g		X ^g	X	X	X	X
Urine Pregnancy test for WOCBP ^h										X	X	X	X
Study drug administration	X	----- X -----											
Dispense study drug	X				X					X	X		
Collect study drug					X					X	X	X	
Telephone contact		X		X		X		X					
Adverse event collection		X	X	X	X	X	X	X	X	X	X	X	X
Clinical chemistry			X		X		X		X	X	X	X	X
BNP and NT-Pro BNP ^{i,j}			X		X		X		X	X	X ^h	X ⁱ	X
Hematology			X		X		X		X	X	X	X	X
Urinalysis and microscopy			X		X		X		X	X	X	X	X
6-min walk test					X					X	X	X	X
██████████					█					█	█	█	█
██████████										█		█	

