9.1.2. Management of Elevated Transaminase Levels (ALT and/or AST)

Nearly all instances of elevated transaminases are expected to be asymptomatic. Check transaminase levels (as well as total bilirubin (TBL), GGT, alkaline phosphatase (ALP), and International Normalized Ratio (INR) within 48-72 hours during an unscheduled visit if the following occurs:

- ALT or AST levels > 3X ULN

Repeat testing every 72 to 96 hours until transaminase levels are below three times the ULN for at least one week or the patient withdraws consent.

Discontinue study drug administration permanently if any of the following occurs:

- ALT or AST > 8X ULN
- ALT or AST > 5X ULN for more than 2 weeks
- ALT or AST > 3X ULN and [TBL > 2 x ULN **or** INR > 1.5]
- ALT or AST > 3X ULN with the appearance of fatigue, nausea, vomiting, right upper quadrant pain or tenderness, fever, rash, and/or eosinophilia (> 5%); The hepatobiliary tree must be visualized (e.g., ultrasound, MRI) and assessed if a patient discontinues taking study drug secondary to elevated transaminase levels. Additional tests/studies may be warranted depending on the clinical presentation.

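### Monitoring after a Part 2 dose increase: Table 6 ends daily weights four weeks early for Cohorts 3-4, and Cohorts 1-2 have no required 4-week laboratory check

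*Protocol*

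**What the plan says.** **Daily weights, Cohorts 3-4.** Protocol Table 6 footnote e has patients weigh themselves daily from Week 16 to Week 20 and weekly after that. Section 9.1.1 (twice) and Section 9.10.8 set eight weeks of close weight monitoring in Part 2 for these cohorts. Section 7.1 lets them increase the dose at Week 20.

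**Laboratory checks, Cohorts 1-2.** Table 5 schedules chemistry and BNP/NT-Pro BNP at Weeks 18, 20 and 32 (NT-Pro BNP alone after that), then every 24 weeks from Week 56. For an increase, footnote i adds: "Patients who dose escalate must have a telephone call 1 week after dose escalation and an unscheduled office visit or home health 2 weeks". The window on that visit is three days either side, and its purpose is to draw chemistry, BNP and NT-Pro BNP. No later draw tied to the increase is required.

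**Expected time course.** Section 5.1.3 says of transaminases: "The elevations begin immediately after initiation of treatment or an increase in dose and peak approximately two to four weeks later". Section 9.1.2 adds: "Nearly all instances of elevated transaminases are expected to be asymptomatic".

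**Whether Cohorts 1-2 may escalate.** The synopsis, Section 7.1, Section 9.7 and Table 5 footnote i allow it in Part 2. Section 7.3 contains both positions: its opening paragraph rules out raising the dose within a patient in these cohorts in either part, and its last sentence permits escalation for all patients at Week 20.

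**The concern.** On weights, a site working from Table 6 would drop daily weighing at the visit where the dose may go up. The five-pound stopping rule in Section 9.1.1 runs for eight weeks of Part 2 in these cohorts, so its second half would rest mainly on weekly home readings.

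On laboratory checks, the required draw for Cohorts 1-2 falls at the start of the period in which Section 5.1.3 expects the peak. A value above 3X ULN at that draw starts close follow-up: "Repeat testing every 72 to 96 hours until transaminase levels are below three times the ULN for at least one week". A patient at or below 3X ULN then, who rises above it later, triggers nothing unless someone draws a sample, and symptoms are not expected to prompt one. The withdrawal thresholds of 8X ULN, and of 5X ULN for 14 days, in Section 8.4 likewise act only on measured values. What is at stake is the safety of individual patients. The efficacy analysis is not touched.

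**Working it through.** The documents state no gap figure to reproduce. The inputs are the visit windows in Tables 4 to 6 and the study days in SAP Table 1.

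**Daily weights, Cohorts 3-4**
- Required by 9.1.1 and 9.10.8: Week 16 + 8 weeks = Week 24 (study day 168).
- Given by Table 6 footnote e: to Week 20 (study day 140).
- Shortfall: 168 - 140 = 28 days, all after the Week 20 option to increase. At one reading a week, 28 / 7 = 4 home readings replace 28.
- Table 6 footnote e gives the same daily-weight period as Table 5 footnote e, where four weeks is correct for Cohorts 1-2. Table 4 footnote f gives Cohorts 3-4 eight daily-weight weeks in Part 1, which spans their Week 4 increase. The Part 2 footnote is the one out of line.

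**Laboratory gap, Cohorts 1-2, increase at Week 20**
- Week 20 = day 140 ± 3 = 137 to 143.
- Week 32 = day 224 ± 5 = 219 to 229.
- Required draw = 14 ± 3 = days 11 to 17 after the increase.
- Increase to Week 32: nominally 224 - 140 = 84 days; range 219 - 143 = 76 to 229 - 137 = 92.
- Required draw to Week 32: nominally 84 - 14 = **70 days**; range 76 - 17 = **59** to 92 - 11 = **81**.
- No draw is required on days 18 to 28 after the increase.

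**Comparison with the planned dose increases**

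| Increase | Draw at 2 weeks | Draw at 4 weeks | Next draw |
|---|---|---|---|
| Cohorts 3-4, Week 4 (Table 4) | Week 6 | Week 8 | Week 12 |
| Cohorts 3-4, Week 20 (Table 6) | Week 22 | Week 24 | Week 32 |
| Cohorts 1-2, Week 20 (Table 5, footnote i) | 2 weeks ± 3 days | none | Week 32 |

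For Cohorts 3-4 the interval from Week 22 to Week 24 is 168 - 154 = 14 days, or 8 to 20 with ±3 days at each visit.

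**Can Week 32 stand in?** Take the latest stated peak, day 28, and the two weeks to resolution that Section 5.1.3 gives for nearly all patients: 28 + 14 = day 42. Week 32 falls on days 76 to 92, so 76 - 42 = 34 to 92 - 42 = 50 days too late to show a typical late peak.

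**Other escalation times.** If the wider permission in 7.1 and 9.7 governs, an increase at Week 32 is checked at Week 34 and then at Week 56: 392 - 238 = 154 days.

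**The case against.** On the weights, Table 6 still has clinic or home-health weights at Weeks 22 and 24 and calls at Weeks 21 and 23, and the body text is clear. That limits the harm but does not make the footnote right.

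On the laboratory check, the other side has more:
- Section 7.3 denies these cohorts any escalation, and its Week 20 sentence closes a paragraph about Cohorts 3-4. The premise survives because four other places allow escalation and footnote i exists to manage it, but the conflict has to be settled first.
- Footnote i is a deliberate safeguard. Days 11 to 17 lie in the rise or early peak, so many later peaks would already be visible. Section 9.7 allows unscheduled tests, and the PSRC meets about quarterly (9.6.3). All of this stands, but none of it requires a draw in weeks 3 to 4.
- By Section 5.1.3 most elevations are mild and self-limiting, and "persistent elevations to above three times the ULN have not been observed". The same section says: "Patients who experienced elevations to greater than three times the ULN sometimes required additional time to resolve". The consequence is therefore small, though not nil.

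A reader might infer more than the documents support:
- That Cohorts 1-2 are the one exception among seven starts and increases. Day 1 in Tables 3 and 4 and Week 16 entry in Tables 5 and 6 do have draws at 2 and 4 weeks, but these four are treatment starts. The like-for-like comparison is the two increases in Cohorts 3-4, which are fixed visits for every patient there.
- That the gap gives a missed-detection rate. Applying the 4 to 11% from earlier studies to all 54 planned patients (38 + 16) gives 2.2 to 5.9, but this assumes everyone escalates and counts elevations at any time. Patients already at 10 mg or more have no increase to make, and the share first passing 3X ULN after the 2-week draw is not given and could be near zero.
- That daily weights must also be extended for Cohorts 1-2. Section 5.1.2 ties fluid risk to treatment initiation in Stage 4 CKD, so carrying it to an increase here is an inference.

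**Conclusion.** The two points stand separately, and neither supports the other.

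1. Table 6 footnote e is wrong as written. It removes 28 days of daily weighing that Sections 9.1.1 and 9.10.8 require in Cohorts 3-4, directly after the Week 20 option to increase. This rests on no assumption.

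2. The missing 4-week draw in Cohorts 1-2 is a minor weakness with a cheap remedy. The gap of 70 days (59 to 81) assumes that these cohorts may escalate and do so at Week 20. The protocol's own peak timing and both planned increases in Cohorts 3-4 favour a second draw. The number of patients exposed is unknown and below 54. The trial's conclusions do not change.

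**What to change.** - **Table 6 footnote e:** run daily home weights to and including Week 24. This costs one footnote and needs no new equipment.
- **Section 7.3:** state whether, and at which visits, Cohorts 1-2 may escalate in Part 2, in agreement with the synopsis, 7.1, 9.7 and Table 5.
- **If they may:** add a chemistry, BNP and NT-Pro BNP draw 4 weeks (±3 days) after each Part 2 increase. Permit home health, and let a scheduled visit at that time count. Amend Table 5 footnote i and the matching text in the synopsis and Section 7.1. The cost is one routine sample per escalating patient. Some mild elevations that would have passed unseen will be found, and any above 3X ULN will start the repeat testing in 9.1.2.
- **Optional:** four weeks of daily weights after an increase in Cohorts 1-2. If adopted, Table 5 footnote e, Section 9.1.1 and Section 9.10.8 must change together, or they will contradict one another.
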